Research Design. This study will evaluate the feasibility and usability of assessing real-time residential environmental exposures (VOCs/PM_{2.5}), asthma symptoms, and lung function using an innovative combination of commercially available technology (Aim 1).⁶⁰ In addition, we will use observational design to explore the unintended effects of these residential environmental exposures on adults with poorly controlled asthma in the era of COVID-19 (Aims 2 & 3).

Sample. Eligibility criteria include GCAS participants who: (1) indicated willingness to be contacted for future research, (2) reported high use of disinfectant/cleaning products since COVID-19 (≥ 5 per week), and current ACT ≤ 19 . Non-US residents and non-English speakers will be excluded. We will strive to have at least 20% of the sample representing minority populations. Fifty individuals meeting these criteria will be randomly selected and invited to participate in this study using their preferred contact method (94% indicated email). Interested individuals will be directed to a REDCap survey link to confirm willingness to participate, verify eligibility, and provide current contact information. We will randomly select replacements if no response is received after 2 contact attempts over two weeks or lack of interest is indicated.

Data collection methods. Three innovative data collection methods will be integrated in this feasibility study: Ecological Momentary Assessment (EMA) downloaded to participants' smartphone, Awair Omni Indoor Air Quality Monitor®, and Zephyr_x Spirometer.

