EMA is a survey approach which uses repeated sampling of participants to capture behaviors and experiences in a real time context. This methodological approach maintains the ecological validity of reported behaviors and decreases the impact of recall bias as surveys are sent periodically to participants through electronic devices.⁶¹ EMA is particularly useful when trying to understand the context around symptoms or behaviors. Available literature that combines the EMA methodology with asthma research focuses primarily on asthma-related outcomes such as symptoms, control, quality of life, history, and medication adherence and their relationship with stress (perceived stress, mood, hassles, social support).⁶²⁻⁶⁴ None of the published literature to date pairs EMA with indoor air quality and asthma symptoms. The ability to timestamp behaviors, events, experiences, whether they present a positive or negative health impact, is valuable when seeking to understand the complexity of multiple risk factors and multiple environmental and behavioral interactions.

Exposure	Sensor	Range/ Accuracy	Optimal range
VOCs	Multi-pixel metal oxide semiconductor gas sensor	0-60,000 ppb/ $\pm 10\%$	<333ppb
PM _{2.5}	Laser-based light scattering particle sensor	0-1,000 $\mu\text{g}/\text{m}^3$ / $\pm 15\mu\text{g}/\text{m}^3$ or 15%	<15 $\mu\text{g}/\text{m}^3$

Awair Omni Indoor Air Quality Monitor® continuously monitors about 1,000 square feet of indoor air for 7 air quality factors: total VOC, PM_{2.5}, temperature, humidity, CO₂, ambient light, and ambient noise. This feasibility study will only focus on VOCs and PM_{2.5} levels (Table 1). The Awair Omni measures about 4"X4"X1.3", is wi-fi and Bluetooth enabled, plugs into a standard AC outlet, and includes an 8-hour battery back-up. An air quality reading is taken every 10 seconds and real-time data are uploaded to a dashboard accessed only by research personnel. The display on the Awair Omni will be limited to VOCs and PM_{2.5} data. Our preliminary work with Awair indoor air quality monitors indicates that increased VOC levels are detected when disinfectants are used and increased PM_{2.5} levels are detected when vacuuming without a

[figure not shown]
[figure not shown]
vacuum cleaner.

HEPA filter. The Awair proprietary dashboard provides secure communication between the Awair Omni and its dashboard. Data will be exported from the dashboard to a .CSV file.⁶⁵⁻⁷¹

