4. During the 14-day data collection period, data from the EMA will be collected using EMA software platform on a personal smartphone (iOS or Android) and EMA software platform.⁷³ Each morning, participants will receive an EMA survey concerning asthma symptoms and a reminder to use their spirometer. Additionally, EMA surveys addressing disinfectant use, asthma symptoms, and spirometry will occur randomly twice/day (6am – 10pm) or tailored for those working off hours (Appendix).
5. A custom interface between the EMA platform and the Awair indoor air quality monitor will alert participants when levels of indoor VOCs or particulates are detected outside the optimal range (Table 1). The air quality monitor will communicate with the EMA platform using publicly available application programming interface (api). Upon notification from the Awair, the EMA will signal the participant to complete a brief survey on disinfectant use/air particulate exposure (depending on the alert), current asthma symptoms, and proximity to the Awair (Appendix). The EMA will then direct participants to use the spirometer. Participants experiencing symptoms will be guided to follow their asthma action plan/provider instructions.
6. Thirty minutes after VOC/PM_{2.5} notification, a second EMA notification will be sent for participants to complete a survey on mitigation strategies, respiratory outcomes, and spirometry use if not already completed (Figure 4).
7. Research personnel will monitor use of these devices/apps and contact participants if a 24-hour gap in data is noted to address concerns and determine acceptability. Research team members will check-in with each participant at about the 7-day mark to address technical concerns and ease of use.

8. At the end of the 14 days, participants will complete a short acceptability, appropriateness, and feasibility REDCap survey. A random sample of 20 participants will be interviewed to provide further insights.
9. Participants will be asked to return the Awair in the provided mailer. The Awair will be fully disinfected per manufacturer's directions. Participants will keep the Zephyr_x spirometer as an incentive.

Baseline Measures

The following measures will be administered at baseline via REDCap:

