- *EMA survey triggered by VOCs/PM_{2.5} greater than optimal range as detected by the Awair* will query asthma symptoms, lists of probable sources of elevated VOCs or PM_{2.5}.
- *EMA survey 30-minutes after Awair air quality notification* queries mitigation strategies used (from lists) and asthma symptoms.
- *Home spirometer use* (Yes:No) queried in each EMA survey

Home spirometer. FEV₁% predicted– a standard metric of lung function for those with asthma.

Seven-Day check-in. Open-ended questions to identify any trouble-shooting areas, determine if adjustments need to be made, and assess ease of use of the app/devices. Interactions will be recorded and reviewed by the research team for patterns and to identify any adjustments that are needed.

Participant feasibility assessment. At the end of the 14-day data collection period, participants will be asked to respond to a short REDCap survey assessing acceptability, appropriateness, and feasibility of the indoor air quality monitor, EMA notifications, and the home spirometer with response ranging from 1=completely disagree to 5=completely agree. A random sample of 20 participants will be interviewed to further explore these factors using open-ended questions such as "Tell us what you liked/didn't like about the indoor air quality monitor", "Describe the strengths/concerns about the survey you received about your home indoor air quality".

Data Analysis

Each day of observation will be divided into four 4-hour periods between 6 a.m. and 10 p.m. Data from a given period will be considered as follows:

1. Period specific data from all event-contingent EMA prompts [prompts triggered by high indoor air VOC/PM_{2.5} readings] will be analyzed. If multiple event-contingent prompts were answered, data will be averaged across all event-contingent prompts during that period.
2. Data from all answered baseline and random [signal-contingent] EMA prompts will be considered.

Aim 1. For this aim, we will assess:

1. Compliance with the EMA prompts as indicated by the frequency of responses to prompts, specifically:
 - a. # of responses (complete:incomplete)/number of prompts
 - b. # times spirometer used/number of prompts
 - c. # times environment modified/number of event-contingent prompts
2. Compliance as described in 1a-1c by 4-hr each period.

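### Aim 3 mixes being told that the air is out of range with being exposed to it, and the planned models do not separate the two

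*Combined protocol and SAP*

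**What the plan says.** Procedures, step 5: the interface between monitor and EMA platform "will alert participants when levels of indoor VOCs or particulates are detected outside the optimal range". The alerted participant is asked to "complete a brief survey on disinfectant use/air particulate exposure (depending on the alert), current asthma symptoms, and proximity to the Awair". Then: "The EMA will then direct participants to use the spirometer". Step 6 adds a second survey half an hour later on mitigation and respiratory outcomes.

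Procedures, step 4: one morning survey and two randomly timed surveys a day are sent whatever the sensor reads.

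Data collection methods, Awair Omni: "The display on the Awair Omni will be limited to VOCs and PM_{2.5} data", whereas "real-time data are uploaded to a dashboard accessed only by research personnel".

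Data Analysis: event-contingent answers are analysed, and averaged where a 4-hour period holds several. Baseline and random answers are to be considered, but how the two kinds are combined is not stated. The Aim 3 exposures are baseline self-report, the weekly count of readings beyond the optimal threshold, and the mean VOC and PM2.5 level per time window. The outcomes are any asthma symptom, inhaler use and FEV1% predicted. Adjustment covers time and weekday at level 1, and baseline symptoms, demographic and psychosocial variables at level 2.

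Research Design describes Aims 2 and 3 thus: "we will use observational design to explore the unintended effects of these residential environmental exposures on adults with poorly controlled asthma".

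**The concern.** At an event-contingent prompt, a Yes/No symptom answer and an effort-dependent FEV1 come from someone who has just been told that the air is out of range. At a scheduled prompt the same person has usually been told nothing. Since the alert is set off by the exposure under study, a higher symptom rate at high exposure could reflect the exposure, the message, or both. Participants come from a survey on disinfectants and asthma and were selected for heavy disinfectant use and ACT of 19 or less, so an expectation effect is plausible.

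The study is meant to supply preliminary data for a powered study, and the Summary says that it may influence recommendations on disinfectant use. A symptom association produced partly by the alert would carry forward into both.

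Aim 2a has a separate and milder problem. It is descriptive and contrasts no groups, but alerts may prompt people to ventilate or stop cleaning, which changes the levels being described. Action after an alert is itself an Aim 1 measure ("times environment modified/number of event-contingent prompts").

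**Working it through.** The plan gives no power calculation, symptom rate or alert frequency, so there is no figure of its own to reproduce.

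**Step 1: passages side by side.**
- Alert trigger: a reading outside the Table 1 optimal range (step 5).
- Aim 3 exposure 2: weekly count of readings beyond the optimal threshold, which I read as the Table 1 range.
- Order in time: alert, then survey, then spirometer (step 5).
- Aim 3 covariates: no prompt type, no alert status.
- Nowhere in the text: an un-alerted period, an analysis of scheduled prompts alone, or a stated limitation on awareness.

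So the alert depends on the exposure, precedes the outcome and has no term in the model.

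**Step 2: data not triggered by the sensor.** Planned maximum: 50 participants × 14 days × 3 scheduled prompts = 2100 prompts. There are 50 × 14 × 4 = 2800 analysis windows.

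**Step 3: how large could the effect be?** All rates here are assumptions, and the true effect is set to zero. Let p be the symptom probability per window, r the chance that a symptom-free participant reports a symptom because of the alert, and s the share of high-exposure windows with alert-informed answers.

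Apparent OR = odds(p + s·r·(1 − p)) / odds(p)

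Example with p = 0.2, r = 0.05, s = 1: 0.2 + 0.05 × 0.8 = 0.24; (0.24/0.76) / (0.20/0.80) = 1.26.

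| p | s = 1, r = 5% | s = 1, r = 10% | s = 0.5, r = 5% | s = 0.5, r = 10% |
|---|---|---|---|---|
| 0.1 | 1.53 | 2.11 | 1.26 | 1.53 |
| 0.2 | 1.26 | 1.56 | 1.13 | 1.26 |
| 0.3 | 1.18 | 1.37 | 1.09 | 1.18 |
| 0.4 | 1.13 | 1.28 | 1.06 | 1.13 |

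**Step 4: would a study of this size pick it up as a finding?** Simulation with no true effect, 2000 runs per setting: 50 people, 56 windows each, assumed 75% response, between-person SD of 1.0 on the logit scale, s = 1, and a Mantel-Haenszel test stratified by person at two-sided 5%. Proportion of runs declared significant:

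| p (typical person) | High-exposure windows | r = 0 | r = 5% | r = 10% |
|---|---|---|---|---|
| 0.2 | 10% | 5.1% | 24.6% | 71.5% |
| 0.2 | 25% | 5.4% | 46.0% | 95.0% |
| 0.3 | 10% | 5.3% | 19.2% | 56.0% |
| 0.3 | 25% | 4.6% | 31.7% | 83.1% |

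These figures contrast high- with low-exposure windows. The plan fits weekly counts and window means, so they show that the mechanism can matter at this size. They do not estimate the bias in the planned coefficients.

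**The case against.** Alerting is deliberate (Specific Aims), response to alerts is an Aim 1 measure, and Aim 3 is exploratory within a feasibility study. That stands: the point limits how Aim 3 can be read and does not touch Aim 1.

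The planned data also allow partial separation. Scheduled prompts do not depend on the sensor, baseline self-report precedes the devices, and window means vary below the threshold too. That also stands, though the plan does not say that it will use it. An earlier alert, or the display, could still inform some scheduled answers.

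Awareness does not come only from the alert. Someone who has just disinfected a room knows it, and the random surveys ask about disinfectant use alongside symptoms. No change to the alert removes this.

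A reader might infer more than the documents support:
- *That the triggered survey asks about exposure before symptoms.* Step 5 lists exposure first, but the EMA survey items section lists symptoms first for the same survey, and the Appendix is not in the text available. Only the alert's place before both is established.
- *That the bias runs toward the study hypothesis.* Aim 3 states none. Mitigation or following the action plan after an alert could lower window means or change FEV1, which is also less open to expectation than a Yes/No item.
- *That participants watch live values throughout.* The display is described, and the unit stays in the rooms used most, so this is a fair inference but is not stated. The alert alone is enough for the point.

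**Conclusion.** The concern holds for Aim 3. Followed as written, the plan mixes being told with being exposed at event-contingent prompts, and no planned term or sensitivity analysis addresses it. Expectation can inflate the symptom association. Under the assumed rates, the spurious odds ratio runs from 1.06 to 2.11, but the real size is unknown because the documents give neither symptom prevalence nor any measure of response to the alert. For FEV1, and wherever participants mitigate, the direction is uncertain.

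The exposures are not affected equally: baseline self-report is not affected, and answers at morning and random prompts are less affected than those at alerts. It would be too strong to say that the two influences cannot be separated at all, or that Aim 2a contains a biased contrast. Aim 2a contrasts nothing; its levels simply describe homes under feedback.

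**What to change.** (a) **Data collection.** Give the event-contingent survey the same neutral invitation as the random survey. Put the brief Yes/No symptom items first, then at once the out-of-range message, then the source, proximity and spirometry steps. Keep all alerts and action-plan wording. The sponsor must ensure that the alert still reaches anyone who does not open the survey.

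(b) **Analysis.** Add prompt type to the Aim 3 models. Report the exposure-outcome associations from scheduled (morning and random) prompts alone beside the pooled result, and state that awareness of exposure limits interpretation. Prompt type tracks exposure closely, so adjustment reduces the problem without removing it. If data collection is over, (b) can still be done.

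(c) **Aim 2a.** Label the VOC and PM2.5 summaries as exposure under feedback.

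**Cost.** Disclosure is delayed by about a minute (an estimate). Masking is only partial, because prompts beyond the scheduled three may be recognised as alerts, and FEV1 still follows the message. The scheduled-prompt analysis has at most 2100 records before non-response, so it is less precise than the pooled one.

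I would not go further and switch off the display or reserve a run-in day without feedback. The documents do not say that the display can be turned off or that alerts run during run-in, and one day soon after sensor calibration is weak evidence of usual exposure.

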As individuals are sheltering at home for longer periods of time, those with asthma may increasingly contend with household asthma triggers and new chemical exposures as they sanitize their home environments to prevent COVID-19. Household asthma triggers may include air pollutants^{6,7} such as air particulate matter in the form of combustible pollutants such as secondhand smoke⁸ and use of different chemical cleaning/disinfecting products.^{9,10} Tight housing construction results in less well-ventilated homes and enhanced exposure to household air pollutants. Ordinarily, adults can spend as many as 15 hours per day indoors^{11,12} which further contributes to their risk for environmental exposures. The current COVID-19 crisis has altered usual cleaning practices and amount of time spent at home. It is unknown how these changes impact adults with asthma.

We will assess the feasibility and usability of ecological momentary assessment (EMA) to capture the context of real time behaviors and environmental exposures that impact indoor environments. In addition, we will assess the feasibility and usability of providing participants with a readily available indoor air quality monitor (Awair Omni®) to continuously capture total volatile organic compounds (VOCs) and particulates (PM_{2.5}). This design will allow us to alert participants of high levels and collect real time data on exposures and asthma symptoms. Daily and exposure-related lung function will be measured with a low-cost home spirometer. Finally, we will examine the effect of residential environmental exposures that may be related to increased time spent at home due to COVID-19 and the associations between these exposures and asthma control.

Our team is comprised of three nurse-scientists and a physician-scientist, each of whom have research focused on asthma experienced in a range of age groups from adolescent to older adult. Our team has established community partners (Chicago Asthma Consortium) and our research team members are situated in three different midwestern US areas. Our long-term goal is to characterize the impact of COVID-19 on existing asthma risk factors so as to develop tailored, home-based asthma interventions that takes into account COVID-19 and are responsive to the changing home environment and change in home routines resulting from this pandemic. For adults with sub-optimally controlled asthma, this study will:

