Zephyr_x Spirometer⁷² system allows for laboratory quality pulmonary function tests (PFTs) at home (FVS-forced vital capacity, FEV₁-forced expiratory volume in 1 second, FEV₁/FVC, flow-volume loop). The system consists of an FDA approved handheld Bluetooth spirometer (MIR Spirobank Smart), and a mobile application that works on a smartphone or tablet device. The MIR Spirobank bank measures 49x109x21 mm and weighs 60.7 g. Participants share PFT results through their app and researcher team members will access a HIPAA compliant portal to view participants' PFT results in real time. An in-App video coaching feature guides the participant through the PFT maneuver. Each maneuver conducted by the participant creates a time and date stamped American Thoracic Society standard PFT report accessible through the portal. Data will be exported from the dashboard to a .CSV file.

Procedures (Figure 3)

1. Randomly selected individuals from the CGAS study who meet eligibility criteria will be invited to participate in the current study. Those interested will be directed to a REDCap link to complete an E-consent form and baseline questionnaire.
2. An Awair Indoor Air Quality Monitor and a Zephyr_x Spirometer will be mailed to each participant along with a quick start guide, written instructions with a link to an instructional video, and research team contact information. Once received, a research team member will conduct a live chat with each participant to enable the devices, download apps (EMA, Zephyr_x), setup and test the devices and apps, review the protocol, and address questions. Participants will be instructed to place the portable Awair air quality monitor in the room where they spend the most time during the day and at night where they sleep.
3. A 3-day run-in period will be completed during which the participants will become familiar with the devices and troubleshoot issues (Awair requires 24-48 hours to calibrate VOC sensors). Study personnel will be available to answer questions/address technical issues. After the run-in period, a research team member will contact the participant to launch the 14-day data collection period.

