1. *Adult Asthma History* includes 5 items adapted from the Behavioral Risk Factor Surveillance System Survey.⁷⁴ Four items address participants' recent contact with healthcare professionals for asthma since COVID-19. The final item addresses changes in routine work/activities due to asthma since COVID-19.
2. *Asthma Control Test (ACT)*. The ACT includes 5 items addressing: asthma symptoms, use of rescue medications, and effect of asthma on daily functioning. Responses are summed for total ACT score.^{75,76}
3. *Airborne Exposures*. The 7 items from the PROMISSM Pool V1.0 Dyspnea Airborne Exposure address airborne allergens, pollutants, smoke, pets, and use of pesticides using Yes:No response options.⁷⁷
4. *Adult Asthma Adherence Questionnaire*,TM includes 5 items on following their prescribed asthma medication plan and barriers to following that plan.⁷⁸
5. *Health and Demographics* includes items such as self-rated physical health, comorbidities, height/weight, age, education, ZIP code, smoking status, and COVID-19 prevention practices, and COVID-19 exposure/infection status.
6. *Home Environmental Exposure* data will be gathered including home type, # of occupants, vacuum with HEPA filter, cleaning practices, cleaning products, air filter, heating, ventilation, smoke exposures, hand washing practices, pests, hobbies, odors, indoor plants, printers, flooring, and stove type.^{79,80}

We will also measure the following psychometrically valid measures as potential confounders:

7. *Emotional Distress-Anxiety and Depression PROMIS Short Forms 4a* assess anxiety and depression levels within the last 7 days (4 items). Higher scores indicate higher severity of anxiety or depression.^{81,82}
8. *Emotional Support*, PROMIS_SF_V2 Short Form 4A measures perceived feelings of support, being cared for and valued (4 items).⁸³ Higher score indicating a higher perceived emotional support.
9. *Perceived stress scale* includes 4 items measuring the degree to which situations in one's life are appraised as stressful.⁸⁴⁻⁸⁶ Higher scores indicate an increased level of perceived stress.

EMA survey items (See Appendix).

- *Asthma symptoms* (trouble breathing, wheezing, coughing, other symptoms [Yes:No]) assessed each time participants are asked to complete an EMA survey.
- *Random EMA surveys (twice/day)* assess use of disinfectants/cleaners in last 2 hours (Yes:No) if Yes, the type, brand, and asthma symptoms are queried.

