We will also assess the duration the indoor air quality monitor is used by each participant. The quantitative participant feasibility assessment of acceptability, appropriateness, and feasibility will be analyzed descriptively. In addition, we will examine differences in use/acceptance by participant characteristics (e.g., age, asthma symptoms, overall health, education, etc). Qualitative interview data will be transcribed, uploaded into Dedoose qualitative analysis software for content analysis.

Aim 2a: We will collect baseline data on the current frequency and degree of disinfectants/cleaners and exposure to environmental triggers (e.g., secondhand smoke). We will capture real-time self-reported data on disinfectant use throughout the study period. We will determine the prevalence of disinfectant/cleaner use and frequency (% EMA prompts at which disinfectant/cleaner use is reported). We will obtain data from the Awair dashboard to determine the number of times VOCs and PM_{2.5} levels exceed optimal levels, average daily levels, average levels per time period, and fluctuations in VOC and PM_{2.5}. We will identify possible environmental triggers that contribute to high levels of VOCs and PM_{2.5} leading to event-contingent prompts.

[figure not shown]
Aim 2b: We will determine baseline level of asthma control as measured by the ACT. We will use EMA to determine the level of asthma control over the study period as indicated by (a) asthma symptoms reported at each prompt and over the 14 days; (b) number of time-periods during which an EMA prompt is sent and participants report asthma symptoms; and (c) lung function as measured by FEV₁% predicted at each prompt. Asthma control will also be evaluated using EMA by exploring differences in variability in lung function.

Aim 3: Data collected using the EMA approach are multilevel with time windows (level 1) nested with individuals (level 2). The exposure variables will include: (1) Baseline self-reported use and frequency of disinfectant/cleaner use and PM_{2.5} exposures; (2) Number of times VOC and PM_{2.5} levels exceed the threshold for the optimal readings per week; and (3) Average scores of VOC and PM_{2.5} levels in the time windows considered in the analysis. The outcome variables we will consider include occurrence of any asthma symptoms, inhaler use, and FEV₁% predicted (within 30 minutes of each EMA prompt).

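### Aim 3 assigns monitor readings to participants whether or not they were near the monitor, so associations with the two monitor-based exposures are likely attenuated by an unknown amount

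*Combined protocol and SAP*

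**What the plan says.** **Monitor.** Under Data collection methods, the Awair "continuously monitors about 1,000 square feet of indoor air". Procedures, step 2, adds: "Participants will be instructed to place the portable Awair air quality monitor in the room where they spend the most time during the day"; at night it goes where they sleep.

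**Surveys.** Procedures, step 5, says that the alert-triggered survey covers the likely exposure, "current asthma symptoms, and proximity to the Awair (Appendix". This is the only mention of proximity. Under EMA survey items, the alert survey "will query asthma symptoms, lists of probable sources of elevated VOCs" or PM2.5, and proximity is not repeated. The random surveys "assess use of disinfectants/cleaners in last 2 hours (Yes:No) if Yes, the type, brand, and asthma symptoms are queried", and no location item is listed. The Appendix with the survey content is not in the available text.

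**Analysis.** Data Analysis, Aim 3, names three exposures: baseline self-report, the weekly number of exceedances of the optimal range, and "Average scores of VOC and PM_{2.5} levels in the time windows considered in the analysis". The last two come from the monitor. The level 1 covariates are time of day and day of week. Proximity appears nowhere in the analysis text for Aims 1 to 3.

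**The concern.** A monitor reading is the participant's exposure only while the participant is in that air. EMA surveys arrive on a personal smartphone, and their timing can be tailored for people who work off hours, so a symptom report can be filed away from home. The baseline questionnaire also asks about other occupants and smoke exposure, so a reading can rise while the participant is out. The plan would still pair that reading with that report.

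The usual result of assigning exposure this way is a slope that is too small. The study is meant to supply preliminary data for a powered study, and an attenuated estimate would mislead its planning. The lag analysis (time from an alert prompt to reported symptoms) is also hard to interpret for an alert that occurred while the participant was elsewhere. Asking about proximity at alerts suggests that the sponsor sees its relevance, yet the plan gives the answer no use.

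**Working it through.** The plan gives no power, effect size or sample-size calculation for Aim 3, so there is no figure of its own to reproduce. The check asks what share of a true within-person slope survives when all windows are used.

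**Inputs from the plan.** Four windows a day over 14 days give 4 × 14 = 56 per person. Fifty participants with complete data would give 50 × 56 = 2,800 windows.

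**Assumed inputs.** The share of time near the monitor, *p*, is set at 0.95, 0.80 and 0.625. All variances and correlations are also assumed.

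**Model.** Let R be the room reading, P = 1 when the participant is near the monitor, and A the exposure when away. True exposure is X = P·R + (1 − P)·A. If P is independent of R, and A has the same variance as R and correlation ρ with it, regressing the outcome on R gives

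estimated slope / true slope = p + (1 − p)ρ.

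- (a) ρ = 0: the ratio is p.
- (b) ρ = 0.5: at p = 0.625 the ratio is 0.625 + 0.375 × 0.5 = 0.81.

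**When presence affects the reading.** Suppose that being near the monitor raises the reading by 1 SD, because the occupant produces emissions. The true slope is −1, and being away shifts the outcome by d units (positive is better). With q = p(1 − p),

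ratio = [p + q + d·q] / (1 + q).

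At p = 0.625, q = 0.234:

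- (c) d = 0: 0.859 / 1.234 = 0.70
- (d) d = −1: 0.625 / 1.234 = 0.51
- (e) d = +1: 1.094 / 1.234 = 0.89
- (f) d = +2: 1.328 / 1.234 = 1.08

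| Scenario | p = 0.95 | p = 0.80 | p = 0.625 |
|---|---|---|---|
| (a) away exposure unrelated to room air | 0.95 | 0.80 | 0.63 |
| (b) away exposure correlated 0.5 with room air | 0.98 | 0.90 | 0.81 |
| (c) occupant raises the reading | 0.95 | 0.83 | 0.70 |
| (d) as (c), outcomes 1 unit worse when away | 0.91 | 0.69 | 0.51 |
| (e) as (c), outcomes 1 unit better when away | 1.00 | 0.97 | 0.89 |

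A simulation of 2,800 windows with 400 runs per cell agrees with rows (a) to (e) to within 0.01. Case (f) rests on the algebra alone.

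**Near-monitor windows only.** In the same simulation the ratio is 0.99 to 1.01 in every scenario. In scenario (a) the standard error rises from 0.096 to 0.098 at p = 0.95, from 0.096 to 0.107 at p = 0.80, and from 0.097 to 0.121 at p = 0.625. At p = 0.625 the slope divided by its standard error improves from 0.63 / 0.097 = 6.5 to 1.00 / 0.121 = 8.3. In scenario (b) it hardly changes: 0.81 / 0.096 = 8.4 against 1.01 / 0.121 = 8.3. The restricted analysis removes the bias here because the model does not let symptoms influence presence.

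**The case against.** **The design already limits the problem.** The monitor is portable and moves with the participant between the main day room and the sleeping room. At 95% presence the loss is about 5% or less in most scenarios. This stands, but it does not cover time out of the home or in other rooms.

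**The Appendix may already ask about location.** A reader might infer that routine surveys definitely omit it. The documents do not show that. The item lists are incomplete: the alert survey's own list leaves out proximity, although step 5 includes it. The fix must therefore be conditional. The lack of any use in the analysis does not depend on the Appendix.

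**Not all of Aim 3 is affected.** A reader might conclude that every Aim 3 exposure effect is diluted. Baseline self-report does not depend on the monitor. FEV₁ comes from a home spirometer, so those readings are probably taken mostly at home; that is an inference, since the device is handheld.

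**A worst case seems available.** A reader might take the statement that "adults can spend as many as 15 hours per day indoors", subtract 8 night hours, and conclude that at least 7/16 = 44% of the effect survives. The documents do not support that bound. The figure describes ordinary times, and Significance says that since COVID-19 those hours have largely been at home. Hours indoors are not hours near the monitor, and the 8 home hours at night are assumed. Nor does a share of time bound the bias if being away is linked to outcomes.

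**Restriction has costs.** It loses windows and may select on behaviour that responds to symptoms or to the alert. There are three routine prompts a day (one morning, two random) but four windows, so an answer about the time since the last survey could span windows. These points stand. They argue against making near-monitor windows the main analysis, but not against reporting that analysis beside the all-windows result.

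**Conclusion.** The point holds for the weekly exceedance counts and the window averages. As written, both are assigned without regard to presence, and no planned analysis can detect or correct this. Attenuation is the likely direction, but its amount cannot be derived from the documents. The ratios 0.95, 0.80 and 0.63 are illustrations that assume 95%, 80% and 62.5% of time near the monitor and away exposure unrelated to room air. Exposure when away that partly tracks room air makes the loss smaller. Worse outcomes when away make it larger. Better outcomes when away can cancel it or turn it into inflation (1.08 in case (f)).

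Aim 3 is exploratory, so no confirmatory conclusion is at risk. What is affected is how the monitor-based associations are read and how they inform the later powered study. The change is still worth making because location at routine prompts cannot be reliably recovered afterwards.

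**What to change.** 1. Unless the Appendix already does so, add one short location item to every EMA survey: near the monitor, elsewhere at home, or away. Refer it to a period that maps to the analysis window, for example since the start of the current 4-hour period. Symptoms are asked in every survey, so a symptom report and a location answer would then come together.
2. For the window-average exposure, prespecify either an exposure-by-proximity term or a near-monitor analysis, reported beside the all-windows result.
3. Use the alert-survey proximity item in the event-based analyses and in the lag analysis from alert to symptoms.
4. If data collection is complete and routine location was not asked, carry out item 3 and state the limitation for routine windows.

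**Cost.** One extra item per routine survey, which matters somewhat because the community advisers' feedback included fewer routine notifications. The near-monitor analysis has a wider standard error (0.107 against 0.096 at 80% presence, 0.121 against 0.097 at 62.5%, in the simulation above). Otherwise the change needs one model term or one additional analysis.
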